#### Investigator Site File / Regulatory Binder

Before site initiation the CRO will provide an Investigator Site File / Regulatory Binder to each study site. The Investigator Site File will include essential documents as defined by the ICH GCP guideline and applicable local requirements.

The investigator will be responsible for the continual update and maintenance of the investigator site file, which will be periodically reviewed by the monitor(s). In case of an audit by the sponsor or an inspection by the Regulatory Authorities these documents will be reviewed.

All study related documents are to be archived and stored according to legal requirements, but at **least for 25 years** after completion of the study.

Prior to destruction the investigator will contact Biotest AG for approval and conformation of such.

## 12.4 Monitoring

The monitor is responsible for checking the quality of data and adherence to the study protocol and to legal and ethical requirements according to local laws and GCP.

The interval between monitoring visits will be dependent on the recruitment rate and the complexity of the study.

Source data verification is an essential part of the monitoring process and the investigator must grant direct access to the subjects' source data.

The extent and nature of monitoring will be described in detail within the monitoring plan.

#### 12.5 Audits and Inspections

Audits will be performed according to the corresponding audit program, including the possibility that a member of the sponsor's quality assurance function may arrange to visit the investigator in order to audit the performance of the study at the study site, as well as all study documents originating there. Audits may also be performed by contract auditors. In this case, the sponsor's quality assurance function will agree with the contract auditor regarding the timing and extent of the audit(s). In case of audits at the investigational site, the monitor, PM-CRO (Project Manager CRO) or CCR (Clinical Manager (cM) Biotest) will usually accompany the auditor(s).

Inspections by regulatory authority representatives and IECs/IRBs are possible at any time, even after the end of study. The investigator has to notify the sponsor immediately of any such inspection. The investigator and institution will permit and support study-related monitoring, audits, reviews by the IEC/IRB and/or Regulatory Authorities, and will allow direct access to source data and source documents for monitoring, audits, and inspections. The principal investigator shall personally participate in all audits and inspections.

## 12.6 Archiving

After evaluation and reporting of the study data, all documents relating to the clinical study will be kept in the archives of the sponsor or of a contracted service provider and the study site(s) according to applicable regulatory requirements.

# 13 GENERAL REGULATIONS, AGREEMENTS AND ORGANISATIONAL PROCEDURES

## 13.1 Study Administrative Structure

Details for the study administrative structure are kept as a separate list filed in the Trial Master File.

## **13.2 Ethical and Regulatory Considerations**

This CSP and any amendments will be submitted to a properly constituted Independent Ethics Committee (IEC) / Institutional Review Board (IRB) and/or Regulatory Authorities (RA), in agreement with applicable regulatory requirements, for formal approval of the study conduct. A copy of these approvals must be submitted to Biotest before initiation of the clinical study and each site needs to keep a copy of these documents.

Changes to the CSP must be made in the form of an amendment that has the prior written approval of Biotest. Substantial CSP amendments need to be notified to/approved by IEC/IRB and/or Competent Authorities (CA) / Regulatory Authorities (RA) prior to implementation as required by applicable regulations.

The clinical study will be performed according to the applicable regulatory requirements taking into account the principles of GCP and the latest version of the Declaration of Helsinki.

PPD

#### 13.3 Committees / Monitoring Boards

Safety data from the clinical study will be evaluated by a DSMB at regular intervals during the study, to ensure that the continuation of the study is appropriate and to make recommendations to the sponsor. The DSMB will consist of permanent members who are not associated with the sponsor or with the operative conduct of the study. A description of the scope of work and operating procedures for the DSMB is provided in the DSMB Charter. The composition of the DSMB will also be outlined in the DSMB Charter.

## 13.4 Written Agreements

A written agreement will be set up between Biotest and each investigator setting out any arrangements on delegation and distribution of tasks and obligations and, if appropriate, on financial matters.

## 13.5 Insurance/Liability

In accordance with the relevant national regulations, the sponsor has taken out a subject liability insurance for all subjects who have given their consent to the clinical study. The subjects are insured against injury caused by study medication or participation. The subjects will be informed about the insurance and their own responsibilities and duties.

The insurance company issuing the policy is defined by the Insurance Certificate for Clinical Trials for the respective county. This certificate will comply with the country-specific legal requirements.

## 13.6 Investigator's Brochure (IB)

The investigator will be informed about current knowledge concerning the study medication BT524 through an Investigator's Brochure (IB). All investigators will be informed immediately about relevant new information available.

## **13.7 Amendments to the Protocol**

Changes to the CSP must be made in the form of a CSP Amendment that has the prior written approval of Biotest. Substantial changes to the protocol need to be notified to/approved by IEC/IRB and/or Regulatory Authorities prior to implementation, as required by applicable regulations.

Amendments in order to eliminate immediate hazard to subjects may be implemented before the approval of the IEC/IRB and/or Regulatory Authorities after consultation with Biotest.

In the event that a significant deviation from the protocol is anticipated based on the subjects status, or occurs due to an accident or mistake, the investigator or his/her designee must contact Biotest or PPD (CRO) at the earliest possible time. This will allow an early joint decision to be made as to whether or not the subject should continue in the study. This decision will be documented by both the investigator and Biotest or PPD (CRO).

## 13.8 Confidentiality

The objectives and contents of this clinical study as well as its results are to be treated as confidential and may not be made accessible to third parties.

Information about study subjects will be kept confidential and managed according to the requirements of the Health Insurance Portability and Accountability Act of 1996. Those regulations require a signed subject authorization informing the subject of the following:

- What protected health information (PHI) will be collected from subjects in this study
- · Who will have access to that information and why
- Who will use or disclose that information
- The rights of a research subject to revoke their authorization for use of their PHI.

In the event that a subject revokes authorization to collect or use PHI, the investigator, by regulation, retains the ability to use all information collected prior to the revocation of subject authorization. For subjects that have revoked authorization to collect or use PHI, attempts should be made to obtain permission to collect at least vital status (i.e. that the subject is alive) at the end of their scheduled study period.

# 13.9 Final Report and Publication

For each study an integrated final report according to ICH-requirements will be produced. At the end of the study the sponsor will provide the competent authority and IEC/IRB with a summary of the CSR **within < 1 year** after the end of the study, where required.

It is generally recommended that the results of clinical studies be presented at congresses and symposia and/or published in scientific journals. Prior to their publication, all results of medical tests with the sponsor's products, and/or publications or lecture manuscripts concerning such results, are to be reviewed and discussed by the coordinating investigator and the sponsor by mutual agreement.

Each investigator is obligated to keep data pertaining to the study secret. He/she must consult with the sponsor before any study data are published.

The legitimate interests of the sponsor, such as acquiring optimum patent protection, coordinating submissions to the health authorities or coordination with other studies in the same field that are underway, protection of confidential data and information, etc. will be given due consideration by all partners involved.

# Final 4.3\_UK

# **15 APPENDICES**

Appendix 1: Safety Definitions Appendix 2: Reporting Procedures

#### Appendix 1: Safety Definitions

#### • Adverse Event (AE)

Any untoward medical occurrence in a patient or clinical study subject administered an IMP and which does not necessarily have a causal relationship with this treatment. An AE may be any aggravation or new unfavorable and unintended sign, symptom, or disease temporally associated with the use of an IMP, whether or not considered related to the IMP.

This includes abnormal laboratory and other investigation results which are considered clinically relevant by the investigator (unless already pre-existing at baseline). However, if an abnormal laboratory value is a sign of an already reported AE (e.g. infection), the respective abnormal laboratory value does not constitute a separate AE.

A surgical or invasive procedure is not an AE in itself. Instead, the condition for which the surgical or invasive procedure is performed may be an AE. Planned or elective surgery or procedures (i.e. planned prior to signature of informed consent) for a pre-existing condition and the pre-existing condition leading to surgery or procedure are not AEs. However, if the pre-existing condition worsened after signature of informed consent, the worsening of the condition constitutes an AE.

Worsening of the disease under study (underlying disease): This will be captured by efficacy parameters and should not usually be recorded as AE, unless one or more of the following criteria are met:

- The worsening of the disease under study constitutes a serious AE
- A deterioration exceeding the usual fluctuations of the disease under study has occurred in the opinion of the investigator
- The worsening leads to discontinuation of the study medication
- Additional treatment is required for the worsening, e.g. concomitant medication is added or changed.

No causal relationship with the investigational drug, or comparator drug, or study procedures is implied by the use of the term "Adverse Event".

## • Adverse reaction of an investigational medicinal product:

All untoward and unintended responses to an IMP related to any dose administered. All AEs judged by either the reporting investigator or the sponsor as having a reasonable causal relationship to a medicinal product qualify as adverse reactions. The expression reasonable causal relationship means to convey in general that there are facts, evidence or arguments to suggest a causal association with the drug.

## • Serious Adverse Event (SAE)

An SAE is any untoward medical occurrence or effect that at any dose\*:

- results in death
  - Death is an outcome of an AE and not an AE in itself. All deaths, regardless of cause or relationship must be reported for study subjects.
- is life-threatening

- "Life-threatening" refers to an event in which the subject was at risk of death at the time of the event; it does not refer to an event which hypothetically might have caused death if it were more severe.
- requires hospitalization or prolongation of existing hospitalization
  - In-subject hospitalization means that the subject has been formally admitted to a hospital for medical reasons, for any length of time, which may or may not be overnight. It does not include presentation and care within an emergency department.
    - A complication that occurs during hospitalization and prolongs the existing hospitalization is an SAE. Complications that occur during hospitalization but do not prolong the existing hospitalization and do not meet any other seriousness criteria are non-serious AEs.
  - Elective or pre-planned (prior to signature of informed consent) hospitalization for investigations, medical or surgical treatment does not meet this seriousness criterion. However, if the underlying condition for which hospital treatment or surgery had been planned worsened during the study, the worsening of the condition is to be reported as SAE.
- results in persistent or significant disability / incapacity
- is a congenital anomaly / birth defect
- is another important medical event
  - Adverse events that may not be immediately life-threatening or result in death or hospitalization but my jeopardize the subject or may require medical or surgical intervention to prevent one of the other outcomes listed above, should be reported as serious. Medical and scientific judgment must be exercised in deciding whether an event is serious.

\* "At any dose" does not necessarily imply that the subject is receiving the study drug at the time of the event.

## • Diagnosis vs. Signs/Symptoms

The investigator should provide a diagnosis rather than individual signs and symptoms, wherever possible and appropriate. However, if there is not enough information to provide a diagnosis, individual signs and symptoms are to be recorded. If a diagnosis is accompanied by unusual symptoms, the diagnosis itself and the unusual symptoms have to be reported separately. For serious and other IRAEs the investigator shall provide any other supporting information that may be required for the assessment of the events, specifically in the free text narrative description of the case. This is of particular importance in situations where a diagnosis cannot (yet) be made. Any subject identifying data on supporting documents (e.g. name, address, phone number) have to be obliterated prior to sending them to the sponsor.

A complication of an AE constitutes another AE. For example in diarrhea leading to dehydration, diarrhea and dehydration would be captured as separate AEs.

The eCRF provides for a number of items to be completed for each AE. This includes the onset date, end date, intensity/severity, seriousness, action taken with study medication, treatment for the AE, outcome, and causal relationship of the AE with the study medication, other drugs, or study procedures.

#### • Onset date, end date

If an AE started during the study but did not end before the final follow-up visit, the investigator must make a reasonable effort to establish the outcome and the end date. If this is not possible, e.g. because the AE is still ongoing, or the subject is lost to follow-up, there will be no end date for the AE.

For all AEs that resolve, resolve with sequelae, or have a fatal outcome, an end date must be provided.

If an AE stops and restarts later, all occurrences have to be recorded separately.

If an AE starts as non-serious AE and becomes serious at a later point in time, the following applies in regard to onset and end dates:

#### • Intensity/Severity

Refers to the extent to which an AE affects the subject's daily activities. Severity will be categorized according to the following criteria:

Mild	The AE does not interfere with the subject's routine activities.
Moderate	The AE interferes with the subject's daily routine, but usual routine activities can still be carried out.
Severe	The AE results in inability to perform routine activities.

 Table: Adverse Event Severity

**Severe vs. Serious:** The severity is used to describe the intensity of an event. This is not the same as seriousness, which is based on subject/event outcome or action criteria usually associated with events that pose a threat to subject's life or functioning. Seriousness, not severity, serves as the guide for defining regulatory reporting obligations.

Example: While an event may be of "severe" intensity, it may be of relatively minor medical significance, such as severe headache. On the other hand, a myocardial infarction would be usually regarded as serious, even if its intensity is "mild".

If formal severity classifications are used, such as the NCI CTC classification used in oncology studies, provisions should be made regarding the reporting of events of defined grading (e.g.  $\geq$  3) as serious.

**AEs with changes in severity:** If an AE changes in severity, this will be captured as one AE with the highest severity grade recorded.

#### • Seriousness

For definition of seriousness criteria refer to section 9.3.1. For a serious AE all seriousness criteria that apply have to be reported. Reporting requirements by the investigator are detailed in Appendix 2.

If a list of always serious terms is to be used in the study, this should be mentioned here, as well as its use by the investigator. For example a PT-based autoseriousness in the eCRF, or an urgent query process once a verbatim is coded to a PT on the list.

## • Action Taken with Study Medication

The action taken with study medication as a result of the AE has to be documented. In the situation that the AE leads to permanent discontinuation of the study medication, this meets the definition of an AE leading to subject's withdrawal from the study, which is an immediately reportable AE (IRAE). Reporting requirements by the investigator are detailed in section Appendix 2.

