## 4.4 Subjects Withdrawal Criteria and Replacements

The participation of an individual subject may be terminated prematurely for reasons such as:

- a. Withdrawal of written informed consent
- b. Study discontinuation due to subject's own request (e.g. personal reasons)
- c. Required treatment with any medication known or suspected to interfere with the IMP
- d. Life threatening thrombosis or TEE or life threatening hypersensitivity or any AE, laboratory abnormality, or other medical condition or situation occurs suggesting that continued participation in the study would not be in the best interest of the subject.
- e. Protocol deviation requiring discontinuation of study treatment
- f. Evidence of exclusion criteria or inclusion criteria not met
- g. Lack of study compliance
- h. Recommendation of the Data Safety Monitoring Board (DSMB)

A subject is entitled to discontinue participation in the clinical study at their own request at any time without stating a reason.

The investigator can terminate a subject's participation in the study at any time if continuation could lead to disadvantages for the subject which cannot be justified by the investigator.

The reason for withdrawal of the subject must be documented by the investigator together with all data collected until the day of premature study termination including laboratory results and assessment of AE. All examinations foreseen for the subject's last study visit (closing visit) should be performed. Afterwards, the subject will be treated according to local standards at the discretion of the investigator.

In case a subject withdraws due to an AE or SAE please follow the instructions given in section 15 Appendix 2: Reporting Procedures of this protocol.

Withdrawn subjects will not be replaced.

For screening failures occurring during the screening period the following data need to be documented in eCRF only:

• Informed consent

- Demographic data
- In-/Exclusion criteria
- End of Study (day and reason)
- AE information

For intra-operative screening failures (not randomized subjects) the following data need to be documented in eCRF only:

- Informed consent
- Demographic data
- In-/Exclusion criteria
- Classification of type of planned PMP surgery (due to underlying cause of the condition, that is the location and extent of the original tumor, including the inability to achieve complete cytoreduction)
- Estimated blood loss
- FIBTEM A10 at Baseline
- Duration of surgery

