# 6.7 Procedures for Emergency Unblinding

In the event of an emergency, each study site will be able to unblind subject treatment allocation via IWRS (either the principal investigator or a designated medic sub-investigator at the study site) without undue delay.

However, unblinding shall only be carried out if a medical emergency requires the identification of the IMP for that particular participant. If the code is broken for a subject (via the IWRS), Biotest must be informed immediately. The reason for opening the code break must be documented on the appropriate eCRF page along with the date and the initials of the person who broke the code.

Any subject for whom the blind is broken will be discontinued from the clinical study, however will be followed-up.

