#### Special precautions for BT524 administration

All plasma-derived human products may lead to allergic or anaphylactic reactions. Thus, the administration of BT524 will be performed under medical supervision where proper medical care for allergic or anaphylactic reactions can be provided. If allergic or anaphylactic-type reactions occur, the infusion must be stopped immediately. In case of anaphylactic shock, standard medical treatment for shock must be applied.

Prothrombin time PT(INR), activated partial thromboplastin time (aPTT), prothrombin fragments  $F_{1+2}$ , thrombin-antithrombin III complex (TAT), D-dimer, PS, PC, antithrombin III (AT III) activity, thrombin time (TT), thrombin generation test (TGT) and further coagulation parameters are monitored regularly to detect a hypercoagulable state.

Changes in vital signs (including pulse [heart rate], blood pressure, respiratory rate, body temperature) are monitored during the surgery and according to the flow chart (see section III).

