# • Immediately Reportable Adverse Event (IRAE)

An AE that must be reported to the sponsor **within 24 hours** of the study site being aware of the AE. Reporting requirements are detailed in Appendix 2.

For this clinical study, IRAEs include

- all SAEs
- all AESIs (serious and **non-serious**)
- all AEs that result in a subject's withdrawal from the study (including suspected allergic reaction)
- Medication error (incl. overdose)
- Pregnancy

Adverse Events Leading to Subject's Withdrawal from the Clinical Study

An AE, serious or non-serious, resulting in subject's withdrawal from the clinical study, i.e., permanent treatment discontinuation (see section 4.4). Reporting requirements by the investigator are detailed in section Appendix 2.

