#### 9.3.4 Assessment of Adverse Events

#### • Responsibilities of Investigator

AEs are assessed by the investigator in a standardized manner including, but not limited to the seriousness, severity, outcome, and causality. This has to be performed in line with the definitions and provisions given in Appendix 1.

Laboratory values outside the reference range have to be assessed for clinical relevance taking into account the pre-treatment values. For reporting of abnormal laboratory values as AEs refer to section 9.2.1.4.

If an AE meets the definition of any of the mandatory AE related stopping rules (section 9.3.1), the investigator must withdraw the subject and report the AE as IRAE according to section Appendix 2. If no mandatory AE related stopping rules defined for the study, delete this sentence.

For all AEs the causality assessment has to be provided in the eCRF, even if based on preliminary data. Once more information is available, the investigator may change a preliminary causality assessment.

During and after participation of a subject in a clinical study the investigator/institution has to ensure that adequate medical care is provided to the subject for any ongoing AEs including clinically significant abnormal laboratory values. The investigator has to inform the subject when medical care is needed for any intercurrent disease of which the investigator becomes aware.

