8.10 Study Visits

The labels of study visits in this study are as following:

- Screening
- Baseline
- Surgery Day 1 (Prior 1st dose)
- Surgery Day 1 (Pre-dose)*
- Surgery Day 1 (15 min after IMP start)
- Surgery Day 1 (90 min after IMP start)
- Surgery Day 1 (End of Surgery)
- Day 2, Follow-up
- Day 3, Follow-up
- Day 5, Follow-up
- Day 8, Follow-up
- Closing Visit
- Early Discontinuation

*only applicable in case of repeated intra-operative IMP administration

For a subject who did not complete the study, date of early discontinuation is the last visit, when the subject discontinued from the study. As subjects are expected to attend a Closing Visit whether they complete or discontinue early from the study, subjects who complete the study will have their Closing Visit data summarized under 'Closing Visit', while subjects who discontinue early from the study will have their Closing Visit data summarized under 'Early Discontinuation'. If a subject terminates the study prematurely without having a closing visit, the data from the last regular visit will be summarized under this visit.

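### The protocol defines stopping IMP for an adverse event as withdrawal from the study, which conflicts with its rule that all treated subjects are followed to Day 36

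*Protocol*

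**What the plan says.** **The definition.** Protocol Appendix 1, under action taken with study medication, says that when an AE "leads to permanent discontinuation of the study medication, this meets the definition of an AE leading to subject's withdrawal from the study", and it makes that AE immediately reportable. Section 9.3.1 describes the same category as an AE "resulting in subject's withdrawal from the clinical study, i.e., permanent treatment discontinuation". Appendix 2 requires that, with such a report, the study completion/termination page of the eCRF be updated as necessary if the AE leads to withdrawal.

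**Withdrawal.** Section 4.4 lists reasons for which participation may be ended. Item (d) begins "Life threatening thrombosis or TEE or life threatening hypersensitivity or any AE" and extends to other situations in which continuing is not in the subject's best interest. On withdrawal, "All examinations foreseen for the subject's last study visit (closing visit) should be performed", after which care follows local standards. Section 6.7 says "Any subject for whom the blind is broken will be discontinued from the clinical study", but the same sentence adds that such subjects will be followed up.

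**Follow-up.** Section 7.1 states, without exception, that all IMP-treated subjects attend Days 2, 3, 5 and 8 and a closing visit at least 5 weeks after surgery. Section 9.3.3 ends the AE and TEAE window at the last study visit.

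**Stopping rules.** Section 9.3.4 tells the investigator to withdraw a subject who meets a mandatory stopping rule in 9.3.1. Section 9.3.1 contains none, and the authoring note "If no mandatory AE related stopping rules defined for the study, delete this sentence" is still in the text.

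**SAP.** Under section 8.10, "subjects who discontinue early from the study will have their Closing Visit data summarized under 'Early Discontinuation" as a separate visit label. Section 12.6.6 builds the virus serology shift table from screening to the closing visit.

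**The concern.** In a trial dosed once or a few times within a single operation, the end of study treatment carries no information about whether a subject should still be observed. Joining the two creates a route by which an adverse event can end the observation meant to detect further events. Section 6.11 instructs, for BT524, "If allergic or anaphylactic-type reactions occur, the infusion must be stopped immediately", so an IMP stop for an AE is foreseeable. Allergic and thromboembolic reactions are the class risks named in 6.11.

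At stake is the completeness of safety data in treated subjects whose IMP was permanently stopped, or whose participation ended under 4.4(d). New thromboembolic events, rebleeds to Day 8, later deaths and late virus serology could go uncaptured. A subject removed because of an early event also contributes less time in which a second event can be seen.

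**Working it through.** **1. The plan's own figure.** Section 9.3.3 puts the last study visit at Day 36, 5 weeks after surgery on Day 1. Check: 36 − 1 = 35 days; 35 / 7 = 5.0 weeks. It reproduces.

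**2. What happens to a treated subject whose IMP is permanently stopped for an AE.**
- Appendix 1 and 9.3.1: the event counts as an AE leading to withdrawal.
- Appendix 2: the study completion/termination page is updated with the report, as necessary.
- 4.4 and the end of 9.3.4: closing-visit examinations should be done. Neither gives a day.
- 4.4: local care afterwards.
- 9.3.3: AE collection ends at that subject's last study visit. After that, only SAEs the investigator considers related are still to be recorded.
- 7.1, read on its own: the same subject attends through Day 36.

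The last line cannot be squared with the others unless the closing examination is held at Day 36, and no passage says so for withdrawn subjects.

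**3. Range of the possible loss.** Assumption: the closing examination takes place on Day d and is treated as the last study visit. Days of routine collection lost = 36 − d; share = (36 − d) / 35.

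| Closing examination | Days lost | Share | Follow-up visits falling after it |
|---|---|---|---|
| Day 1 | 36 − 1 = 35 | 100% | Days 2, 3, 5, 8 |
| Day 2 | 36 − 2 = 34 | 97% | Days 3, 5, 8 |
| Day 8 | 36 − 8 = 28 | 80% | none |
| Day 36 | 36 − 36 = 0 | 0% | none |

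**4. Number of subjects.** The documents give no expected rate of IMP-stopping AEs, code breaks or 4.4(d) terminations. No overall loss or between-arm bias can be calculated.

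**5. The alternative reading also leaves a problem.** Suppose the subject stays to Day 36. SAP 8.8 then counts a completer, while under the protocol's definition the AE belongs in the SAP 12.6.1 rows for events leading to discontinuation from the study. Section 12.6.1 has no row for AEs leading to discontinuation of IMP, so the tables could not tell the two apart.

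**6. Serology.** Closing examinations include virus serology, so a withdrawn subject can still have a sample, only earlier. SAP 8.10 files it under 'Early Discontinuation' and 12.6.6 names only the closing visit. Whether such samples enter the shift table is not stated; the table specifications are a separate document.

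**The case against.** A reader might infer that subjects with an allergic or thromboembolic reaction leave the 5-week follow-up, and that safety results will look too favourable. The documents do not support that, for these reasons.

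- Section 7.1 requires all treated subjects to attend to Day 36. Section 7.2 asks for every effort to obtain a closing visit after early discontinuation, and 9.3.4 repeats the request for last-visit examinations.
- Section 9.3.4 follows serious, severe or related AEs to resolution, with extra visits if they are ongoing at the last visit.
- The Appendix 1 sentence classifies an event for reporting. It does not say that visits cease.
- Stopping an infusion is not necessarily permanent: section 6.3 foresees an interruption for an AE, and SAP 12.3.1 counts interruptions.
- A post-operative thromboembolic event cannot stop IMP, because none remains to be given. It can end participation only through 4.4(d), which is permissive and for thrombosis names life-threatening events.
- Unblinded subjects are expressly to be followed up.
- Early serology is not peculiar to withdrawn subjects: with a telephone closing visit, anyone's sample is taken at discharge (section 7.1).
- The template sentence in 9.3.4 refers to rules that do not exist, so it triggers no withdrawal.

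All of this stands and rules out a claim of documented loss. It does not close the gap. Section 7.1 does not say that its visits survive withdrawal. The closing-visit safeguards carry no date and do not secure Days 2, 3, 5 and 8. Following known AEs does not capture new ones. Section 6.7 does not say which visits its follow-up comprises. The link in Appendix 2 to the termination page makes the definition more than a reporting label.

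**Conclusion.** The point holds as an unresolved contradiction. Confidence is high that the definitions equate IMP discontinuation with study withdrawal and that this conflicts with section 7.1. Confidence is only moderate that follow-up would in practice be shortened, since that depends on how a site reads the conflict.

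For an affected subject, the loss of routine event capture lies between 0 and 35 of 35 days, set entirely by the unstated date of the closing examination. The upper end assumes closing on Day 1 and no later visits. With no event rates in the documents, neither the size nor the direction of a between-arm bias can be stated. Sample size, alpha and the non-inferiority margin are not affected. This is a cheap clarification that protects the safety results.

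**What to change.** **Protocol.** Reconcile 4.4, 6.7, 9.3.1, 9.3.3, 9.3.4 and Appendix 1 with section 7.1:
- Define 'IMP discontinued' and 'withdrawn from study' as separate categories. Both can remain immediately reportable.
- State that IMP-treated subjects whose IMP is stopped, or whose blind is broken, remain in the visits already scheduled and in AE collection to Day 36, unless consent is withdrawn or the investigator ends participation in the subject's interest. When IMP should be stopped is outside this point.
- For those who are withdrawn, say when the closing examinations take place and when AE collection ends.
- Remove the template sentence on mandatory stopping rules in 9.3.4, or reconcile it with 9.3.1, which lists none.

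**SAP.** In 8.10 and 12.6.6, state that serology filed under 'Early Discontinuation' is included in the viral shift table, with its study day.

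**Cost.** A wording amendment and two SAP lines. No new visits or tests are added. The downside is a little extra data collection in a few subjects.
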